6.2 Visit 2 – Procedure visit

Consent for and surgical removal of keloid will be performed in accordance with current standard of care. Keloid excision sample will be sent to pathology per standard of care.

6.3 Visits 3 and 4

Scheduled clinic visits will be at 2 and 4 weeks after the surgical excision (weeks 3 and 5 after initiation of Imiquimod). At these visits, the following will be recorded:

- Subject compliance with therapy – if doses were missed
- The investigator will evaluate for evidence of keloid recurrence
- The investigator will rate the local site reaction on the following scale:
 - None
 - Mild reaction (slight redness, discomfort, no swelling, no ulceration)
 - Moderate reaction (redness, pain and swelling, no ulceration)
 - Severe reaction (redness, pain, swelling, and ulceration)
- The dose of Imiquimod will be adjusted to according to the following algorithm:
 - If intolerable at 5 days per week; stop completely for 1 week then restart but at a reduced dose of 3 days per week. Increase to 5 days per week as soon as tolerable.
 - If intolerable at 3 days per week, a further week off, start again at 3 days per week. Stop if intolerable.
- Any new medication usage and health service usage data will be recorded.

6.4 Visit 5

Last scheduled clinic visit will be at 8 weeks after surgical excision (3 weeks after completing Imiquimod therapy). The investigator will evaluate for evidence of keloid recurrence at this visit and evaluate for any local site reactions per above.

If treatment of the lesion with Imiquimod is stopped because of local toxicity, this will prompt an unscheduled clinic visit so that the dose adjustment algorithm can be implemented.

If at any point during the treatment phase, the keloid is judged to have recurred, then the subject will progress immediately to intralesional injection or re-excision in accordance with current standard of care.

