1.1 Background

Keloids are benign dermal fibroproliferative tumors that represent a form of abnormal wound healing following any insult to the deep dermis, including lacerations, abrasions, surgery, piercings, vaccinations, and burns in predisposed individuals (1). They are distinguished from hypertrophic scars, another type of abnormal scar formation, by their extension beyond the borders of the original wound, failure to regress spontaneously, and tendency to recur following excision (1).

Keloids tend to occur more frequently in dark-skinned individuals, with an incidence of up to 16% in those of black and Hispanic backgrounds (2). These lesions appear to affect male and female subjects equally and most commonly occur in persons aged 10-30 years (2). They typically form on the ears, face, chest, and shoulders and can cause pain, burning, itching, and restriction of motion. Furthermore, the scars can be extremely disfiguring and potentially cause significant social and psychological distress in affected individuals.

The process by which keloids develop is poorly understood, though most theories of keloid etiology relate to fibroblast dysfunction (2). These lesions are difficult to treat, as they frequently recur following excisional removal. Current treatment options include surgical excision, laser, intralesional injections, pressure and silicone dressings, topical preparations, oral agents, radiation, and cryotherapy (1). Oftentimes, surgical excision is combined with adjuvant therapies such as corticosteroids and immunomodulators at the time of skin closure because surgical excision alone has recurrence rates ranging between 45% and 100% (3). Additionally, because surgical excision requires complete removal of all abnormal tissue, post-excision keloid recurrence may lead to a larger keloid than prior to excision. Although many adjuvant therapies to surgical excision and modalities for keloid removal have been proposed, there has been no consensus regarding how to best treat these lesions, and there is currently no medication approved for the indication of reducing keloid recurrence after excision.

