1.5 Dose Rationale and Risk/Benefits

Once daily application of 5% Imiquimod cream is currently approved by the FDA for the treatment of many skin disorders. Although the exact mechanism of action has not been elucidated, when used to treat pre-cancerous lesions and skin cancers, Imiquimod results in inflammation, which destroys the lesion and can result in complete regression. Additionally, as mentioned above, Imiquimod has been shown to be effective in preventing recurrence after surgical keloidectomy, though to a varying degree depending on the site of the lesion.

The proposed dosage regimen for this study is in accordance with the current recommended dosing for superficial basal cell carcinoma – apply once daily before bedtime 5-times per week for a total of 6 weeks. This regimen has been shown to be safe, tolerable as well as effective in inducing molecular and clinical responses in patients.

Areas treated with imiquimod may become inflamed. The symptoms may include itching, burning, redness, ulceration (sores), scabbing, flaking, and pain. There could be increased sensitivity to the sun in areas of drug application. This could be avoided by proper sun protection such as wearing protective clothing and/or applying sunscreen of SPF 30 or greater 15 minutes prior to sun exposure with reapplication every 2 hours. Systemic side effects may include “flu-like” symptoms such as fever, fatigue, headache, nausea, diarrhea, and muscle pain. These symptoms are less common and are generally mild.

Unlike previously reported studies, this study aims to initiate treatment with Imiquimod one week prior to keloidectomy. Our preclinical data suggests that pre-treatment with Imiquimod prior to injury increases wound healing and decreases scar formation. Additionally, it has been shown that when using

CONFIDENTIAL

corticosteroids as an adjunct to surgical excision, it is best to initiate treatment in the preoperative period and continue treatment for up to 3 months post-excision (14).

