Because the effects of the drug are not well studied in pregnancy and during breastfeeding, it is possible that there are harmful side effects that are not yet known to both the mother and unborn or breast-feeding child. Therefore, pregnant and breastfeeding subjects are excluded from the study. Additionally, the risks of this study includes risks of breach of confidentiality. While every effort will be made to protect the confidentiality of study subjects, there is a potential risk of an inadvertent or unintended breach of confidentiality.

As demonstrated in patients who have used 5% Imiquimod for other FDA approved indications, risks of topical application of 5% imiquimod are minimal. Additionally, previous studies as well as our preclinical data indicates that 5% imiquimod could modulate wound healing and prevent keloid recurrence in patients when applied prior to keloid-excision and continued after the procedure. Therefore, we believe that the benefit of possible decrease in keloid recurrence outweighs the minimal risks posed by topical 5% imiquimod therapy.

2 Study Objectives

Primary Objective

To assess the efficacy of 5% Imiquimod cream on preventing keloid recurrence after excision. Subjects will be evaluated by a consultant dermatologist at 2, 4, and 8 weeks following excision and by phone 12 weeks after excision to assess for clinical evidence of lesion recurrence.

[figure not shown]
Secondary Objectives

To assess the safety and tolerability of 5% Imiquimod in subjects undergoing keloid excision. Subjects will be evaluated by a consultant dermatologist at 2, 4, and 8 weeks following excision to assess for local site reaction such as redness, discomfort, swelling, and ulceration.

3 Study Design

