3.2 Primary Study Endpoints

To assess the efficacy of 5% Imiquimod cream on decreasing keloid recurrence after excision when initiated prior to excision

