Diagnosis of keloid will be made clinically by a Dermatology attending in the University of Pennsylvania Dermatology outpatient clinic. If the patient meets all inclusion and exclusion criteria set by the study and wishes for the keloid to be surgically removed, the patient will be approached by the Dermatology team for recruitment into the study. The patient will be given the opportunity to have a further discussion about the study and receive answers to any questions they may have. If the patient is agreeable to participating in the study, written and informed consent will be obtained from the patient or the patient's legally authorized representative. A medical history will be taken, demographic data will be collected, and photo-documentation of the lesions will be recorded.

A urine pregnancy test will be conducted prior to receiving study drug, for all female subjects of childbearing potential who are not postmenopausal > 1 year or surgically sterile. Subjects with a positive urine pregnancy test will be excluded from the study. Subjects will be asked to use contraception during treatment period. If

CONFIDENTIAL

indicated, (missed period, unprotected sexual intercourse, or Investigator discretion), a urine pregnancy test may be administered subsequently at the discretion of the Investigator.

A procedure appointment will be made for the surgical keloidectomy, and the subject will be instructed to apply Imiquimod 5% daily Monday to Friday the week prior to the scheduled excision date. The cream should be left in place for approximately 8 hours. The treatment area should include a 1 cm margin of skin around the tumor. The diameter of cream droplet applied should range from 5 mm to 10 mm for keloid areas of 0.5 cm to 5 cm, respectively.

The subject will also continue applying 5% Imiquimod daily as instructed for 5 more weeks after surgery. Subjects will be followed-up in the outpatient clinic at 2, 4, and 8 weeks post-excision and by phone 12 weeks post-excision.

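### Recurrence has no criterion and no primary time point, two of its three clinic assessments fall on imiquimod, and a false early call cannot be corrected later

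*Combined protocol and SAP*

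**What the plan says.** Section 3.2 states the primary endpoint as an aim: "To assess the efficacy of 5% Imiquimod cream on decreasing keloid recurrence after excision when initiated prior to excision". Section 2 has subjects examined at 2, 4 and 8 weeks and telephoned at 12 weeks "to assess for clinical evidence of lesion recurrence". For Visits 3 and 4, Section 6.3 adds only "The investigator will evaluate for evidence of keloid recurrence"; Section 6.4 is no more specific for Visit 5.

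On timing, Section 6.3 says "Scheduled clinic visits will be at 2 and 4 weeks after the surgical excision", while under Section 6.1 the subject will "continue applying 5% Imiquimod daily as instructed for 5 more weeks after surgery". Section 1.5 warns: "Areas treated with imiquimod may become inflamed". The reaction scale in Sections 3.4 and 6.3 grades redness, pain, swelling and ulceration at the same visits, but nothing links the grade to the recurrence call.

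Section 1.1 does contain distinguishing features. Keloids are told apart from hypertrophic scars "by their extension beyond the borders of the original wound, failure to regress spontaneously", and by a tendency to recur after excision. Section 4.1 item 5 uses similar features for entry; no section requires them when recurrence is called.

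Section 6.4 covers what follows a positive call: "If at any point during the treatment phase, the keloid is judged to have recurred", the subject goes at once to injection or re-excision. Section 4.4.1 also lists recurrence as a reason to stop imiquimod. The study is unblinded (5.8), and photographs are optional in the Section 6 schedule.

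**The concern.** The trial's one efficacy figure is a percentage with a 95% interval (7.2), and every count in it rests on a judgement for which the plan sets no standard. Three features make this more than missing detail.

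- **Timing.** Two of the three clinic assessments are made on the drug. Itch and pain are possible drug reactions (1.5, 3.4) and also possible keloid features (4.1 item 5). Failure to regress can hardly be shown two weeks after surgery.
- **Irreversibility.** Once a site has been injected or re-excised, its untreated course can no longer be observed.
- **Undefined counting.** Section 3.2 does not say whether the rate means recurrence at any visit or status at 8 or 12 weeks, so it is open how an early call enters it. Section 7.3 analyses only those who completed the protocol, so a patient called recurrent early and taken off the drug might leave the denominator.

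At stake is whether the observed rate can be read against the 70% used for planning.

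**Working it through.** **Inputs.** From 7.1: reference recurrence 70% at 8 weeks, expected 25%, power 80%, alpha 5% (sidedness not stated), 8 evaluable, 10 enrolled after about 20% withdrawal. From 6.1 and 6.3: five post-excision dosing weeks; assessments at 2 and 4 weeks (on drug) and at 8 weeks (3 weeks off drug).

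**1. The plan's own figure.** One-sample normal approximation, two-sided 5%:

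n = [(1.960·√(0.70·0.30) + 0.842·√(0.25·0.75)) / (0.70 − 0.25)]² = 7.87, so 8; and 8 / 0.80 = 10. Both figures reproduce.

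**2. What one call does.** This needs no assumed error rate. One patient in 8 is 1/8 = 12.5 points. Exact (Clopper-Pearson) 95% intervals:

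| Recurrences | Rate | 95% interval | Contains 70%? |
|---|---|---|---|
| 1/8 | 12.5% | 0.3% to 52.7% | no |
| 2/8 | 25.0% | 3.2% to 65.1% | no |
| 3/8 | 37.5% | 8.5% to 75.5% | yes |

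The planned result is 0.25 × 8 = 2 recurrences, so a single false call crosses the line. Section 7.2 names no interval method, and 3/8 is close to the boundary. The simple normal interval reaches 0.375 + 1.96·√(0.375·0.625/8) = 71.0%. The Wilson upper limit is [0.375 + 3.84/16 + 1.96·√(0.375·0.625/8 + 3.84/256)] / (1 + 3.84/8) = 69.4%, just below 70%.

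**3. Upward error (illustration).** Assume a false-call probability f at each on-drug visit, independent visits, an endpoint of recurrence at any visit, and no missed recurrences. For true rate p:

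observed rate = p + (1 − p)·[1 − (1 − f)²]

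- p = 25%, f = 5%: 0.25 + 0.75 × 0.0975 = 32.3%.
- p = 25%, f = 10%: 0.25 + 0.75 × 0.19 = 39.2%.
- p = 90%, same f: 0.90 + 0.10 × 0.0975 = 91.0% and 0.90 + 0.10 × 0.19 = 91.9%.

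**4. Downward error (illustration).** If a share m of true recurrences is missed by the end of follow-up and there are no false calls, the observed rate is p·(1 − m). For p = 70% and m = 10%, 20%, 30% this is 63%, 56%, 49%. Here m is what remains missed after the 8-week visit.

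**5. Completers only.** If one of two recurrent patients in 8 were called early and dropped under 7.3, 2/8 = 25% would become 1/7 = 14.3%.

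**The case against.** The assessors are consultant dermatologists (Section 2) who grade the local reaction separately at the same visit. Itch and pain are only optional keloid features in 4.1, and redness and swelling are not listed there. The 8-week visit is off drug and matches the time point of the 70% reference. Early calls could also be examined afterwards by reaction grade, and photographs may exist. All of this is fair. It makes error less likely and partly repairs missed recurrences, but it gives no written standard and cannot undo a false call on a re-treated site.

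The illustrative sizes also deserve the criticism that the 5% to 10% false-call rates have no source in the documents. They matter mainly if the true rate is near 25%. Table 1 in Section 1.4 shows post-excision imiquimod recurrence of 8/9 and 9/9 on the trunk, 3/3 presternal and 4/4 on extremities. At such rates false calls barely move the result.

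Four stronger readings are tempting, and the documents do not support them:

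- That the drug is inflaming the site at Visits 3 and 4. Section 1.5 says only that it may; what is certain is that dosing is scheduled to continue.
- That the data will be a bare yes/no that no analysis can repair. No case report form is shown and no response format is stated.
- That the rate cannot be compared with the 70%. Section 7.1 gives neither the source nor the definition behind that figure, so comparability is unknown.
- That requiring extension beyond the scar border would settle the matter. Cream also covers a 1 cm margin (5.2, 6.1), so drug swelling could cross that border too. The feature helps against a confined raised scar, less against a reaction.

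**Conclusion.** The concern holds in this form: the primary endpoint lacks an event criterion and a time point, two of three clinic assessments are made on drug without blinding, and a false treatment-phase call is final in practice. The firm size is 12.5 points per patient at 8 evaluable, enough for one call to move the exact interval from excluding 70% to including it. That crossing assumes an exact interval and a result near the planned 25%. The 32% to 39% range is illustration only. The plan does not establish the direction of the net error: false early calls push the rate up and cannot be corrected, whereas missed recurrences push it down and the 8-week visit can partly recover them. The sponsor should act on this before the first post-excision visit, because measurements not taken then cannot be obtained later.

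**What to change.** Amend 3.2, 6.3, 6.4 and 7.2 (and 7.3 for the denominator). These changes affect endpoint recording and counting only; decisions about patient care stay as they are.

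1. Define the primary rate as recurrence by the 8-week off-drug visit, the time point of the 70% reference.
2. At Visits 3 to 5, record the ruler width and height of any raised tissue, whether it extends beyond the excision scar border (the feature in 1.1), and the local reaction grade at that visit.
3. Keep every patient called recurrent and re-treated in the denominator and count each as a recurrence in the primary rate. Leaving them uncounted would turn re-treated patients into successes and favour the drug.
4. Report sensitivity rates that reclassify or exclude on-drug calls that did not meet the border criterion or coincided with a moderate or severe reaction. Report the 12-week telephone recurrence separately, since no criterion based on examination can be applied there.

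The cost is a few protocol sentences, a few form fields and a ruler measurement for 10 patients; the sample size does not change. Some early calls will remain uncertain, and that uncertainty will show only in the sensitivity range.

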6.5 Phone follow-up (Encounter 6)

Patient will be contacted by phone 12 weeks after surgical excision of keloid (7 weeks after completing Imiquimod therapy). Patient will be asked about recurrence of keloid at excision site and any residual local site symptoms from Imiquimod therapy.

CONFIDENTIAL

7 Statistical Plan

7.1 Sample Size Determination

In this open-label, single-arm pilot study, 10 patients will be enrolled.

The sample size calculation was based on a historical recurrence rate of 70% at 8 week follow-up after excision alone and an expected 25% recurrence rate with Imiquimod treatment. Using 80 % power and $\alpha = 5\%$, the estimated sample size required is 8. Allowing for a withdrawal rate of approximately 20 %, 10 subjects will have to be enrolled.

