5.9.4 Return or Destruction of Study Drug

At the completion of the study, subjects will be asked to return all unused medication at the final follow-up visit. There will be a final reconciliation of drug shipped, drug consumed, and drug remaining. This reconciliation will be logged on the drug reconciliation form, signed and dated. Any discrepancies noted will be investigated, resolved, and documented prior to return or destruction of unused study drug. Drug destroyed on site will be documented in the study files.

CONFIDENTIAL

6 Study Procedures

Patients will be recruited through the routine work of the Dermatology departments at the Hospital of the University of Pennsylvania. Recruitment and consent will be obtained by the principle investigator or another Dermatology physician as delegated by the investigator seeing the patient in the outpatient clinic. Patients seen in the outpatient clinic with clinical representation of keloids will be approached by the Dermatology attending as part of clinical evaluation, and written, informed consent will be obtained from the patient prior to any research related procedures are conducted.

It will be explained to the potential participant that entry into the trial is entirely voluntary and that their treatment and care will not be affected by their decision. It will also be explained that they can withdraw at any time. In the event of their withdrawal it will be explained that their data collected so far will be retained and used as part of the study analysis.

	Visit 1 (Week 1)	Visit 2 (Week 2)	Visit 3 (Week 4)	Visit 4 (Week 6)	Visit 5 (Week 10)	Phone encounter (Week 14)
Informed consent	X					
Urine pregnancy test	X					
Imiquimod application	X (start after visit)	X	X	X		
Keloid excision		X				
Excision specimen sent to pathology per SOC		X				
Photograph of lesion	X (optional)	X (optional)	X (optional)	X (optional)	X (optional)	
Evaluation of local site reaction		X	X	X	X	
Evaluation for recurrence			X	X	X	X

6.1 Visit 1

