7.2 Statistical Methods

Response rate will be presented as a percentage, with 95% confidence intervals. Other endpoints will be presented descriptively, with an appropriate measure of variation (e.g. standard deviation) if necessary. Patient demographics will be summarized.

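### Section 7.1 dates the 70% reference at 8 weeks, but recurrence is assessed up to a 12-week phone report, no section fixes which contact sets the primary rate, and 7.3 can drop subjects with a known outcome

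*Combined protocol and SAP*

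**What the plan says.** - **7.1** takes "a historical recurrence rate of 70% at 8 week follow-up after excision alone" as its reference and expects 25% with imiquimod, with no separate date for the 25%. With 80% power and alpha 5% it arrives at 8 subjects, and at 10 after allowing for about 20% withdrawal.
- **Section 2, primary objective**, has recurrence assessed in clinic at 2, 4 and 8 weeks "and by phone 12 weeks after excision to assess for clinical evidence of lesion recurrence". The schedule in section 6 marks a recurrence evaluation at Visits 3, 4 and 5 and again at the Week 14 phone contact.
- **6.4**: "Last scheduled clinic visit will be at 8 weeks after surgical excision". **6.5**, on the later call: "Patient will be asked about recurrence of keloid at excision site". No examination goes with the call.
- **3.2**, the primary endpoint, reads "To assess the efficacy of 5% Imiquimod cream on decreasing keloid recurrence after excision when initiated prior to excision". It is an aim without a time point.
- **7.2**: "Response rate will be presented as a percentage, with 95% confidence intervals". It gives no time point, no definition of response, and no test.
- **7.3** restricts the analysis to subjects who finished the protocol. **4.3**, **4.4.1** and **section 6** each say that data gathered before a withdrawal will be kept and analysed, and **4.4.2** asks for the 12-week call even from those who withdraw.

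**The concern.** Two things that define the primary rate are left open: when recurrence stops being counted, and who is in the denominator.

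On timing, 7.1 points to the 8-week examination and section 2 points to the 12-week call. The two contacts also differ in kind: one is an investigator's examination, the other a patient's answer by phone. A reader who follows section 2 will put a 12-week rate beside a reference dated four weeks earlier.

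On the denominator, 7.3 does not say whether a missed call makes a subject a non-completer, or whether a subject who stopped imiquimod early because of recurrence (a reason listed in 4.4.1) has completed. Read literally, it could remove people whose outcome is already recorded.

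The study is open-label and has ten subjects. If these choices are made after the outcomes are known, they can alter the reported rate and its interval noticeably.

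**Working it through.** **1. The plan's own figure.** Inputs from 7.1: reference p0 = 0.70, expected p1 = 0.25, alpha 5%, power 80%. Sidedness and test are not stated; a two-sided one-sample normal approximation is assumed.

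n = [(1.960·√(0.70·0.30) + 0.842·√(0.25·0.75)) / (0.70 − 0.25)]² = [(0.898 + 0.364)/0.45]² = 7.87, rounded up to 8. Enrolment: 8/(1 − 0.20) = 10.

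Both figures reproduce. The arithmetic in 7.1 is sound for an 8-week comparison.

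**2. The clock.** In the schedule, Visit 1 is Week 1 and excision is Week 2. Eight weeks after excision is Week 10 (Visit 5). Twelve weeks after excision is Week 14 (the call). The 70% therefore belongs to Visit 5, and the last recurrence assessment comes four weeks later.

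**3. Direction of the timing effect.** For a fixed set of subjects, recurrences by 12 weeks = recurrences by 8 weeks + those first reported between 8 and 12 weeks. The second term cannot be negative, so the cumulative 12-week rate is at least the 8-week rate.

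**4. Size, as a sensitivity illustration.** 7.2 names no interval method. Exact (Clopper-Pearson) limits are assumed, on the recurrence rate: lower = Beta quantile 0.025 with parameters (x, n − x + 1); upper = Beta quantile 0.975 with parameters (x + 1, n − x).

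| Situation | Count | Rate | Exact 95% interval |
|---|---|---|---|
| Three recurrences by 8 weeks | 3/10 | 30% | 6.7–65.2% |
| One more, first reported by phone | 4/10 | 40% | 12.2–73.8% |
| Three recurrences, one recurrence-free subject dropped under 7.3 | 3/9 | 33% | 7.5–70.1% |
| Four recurrences, two of those subjects dropped under 7.3 | 2/8 | 25% | 3.2–65.1% |

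Row 2 against row 1 is the timing effect: 10 percentage points for one subject. Row 3 against row 1 shows 7.3 raising the rate. Row 4 against row 2 shows it lowering the rate, from 40% to 25%.

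Wilson intervals give the same picture with different limits, for example 16.8–68.7% for 4/10 and 23.7–76.3% for 5/10.

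**5. If 12 weeks were made primary.** The documents give no excision-alone rate at 12 weeks. The 45–100% in 1.1 carries no time point, and every series in Table 1 is imiquimod-treated. Using the formula in step 1 with assumed rates:

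- p1 held at 25%: a reference of 60% needs 15 (enrol 19); 80% needs 5 (enrol 7).
- p0 held at 70%: a treated rate of 30% needs 11 (enrol 14); 40% needs 20 (enrol 25).

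So 7.1 could not simply be carried over to 12 weeks.

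**The case against.** **It is a descriptive pilot, and 8 weeks is evidently meant.** 7.2 plans an estimate with an interval and no success rule, and the date in 7.1 does suggest an 8-week endpoint. Both points stand. But no endpoint or analysis section says so, and the primary objective includes the later call. If 8 weeks is intended, one sentence settles it.

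Four stronger readings are tempting, and the documents do not carry them.

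- **That the trial succeeds or fails on whether the interval excludes 70%.** 70% is the reference used for the sample size. Nothing makes it a decision rule, so the table above shows sensitivity and not reversed conclusions.
- **That the timing mismatch flatters imiquimod.** Under cumulative counting it does the opposite: it could hide an effect but could not create one. Movement in either direction comes from 7.3.
- **That the 10-week availability criterion is an error because it ends before Week 14.** Its starting point is not stated. Counted from Visit 1 it reaches Visit 5 and so covers every clinic visit. The call needs no attendance, and 4.4.2 seeks it even from withdrawn patients.
- **That status at the call might replace the recorded history, so that a treated recurrence is recounted as clear.** On recurrence, 6.4 says "then the subject will progress immediately to intralesional injection or re-excision in accordance with current standard of care", but only for the treatment phase, and 4.4.1 concerns stopping imiquimod early. Nothing suggests that a recorded recurrence would be undone.

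It is also fair to say that choosing 8 weeks demotes a time point in the sponsor's own primary objective, to one only three weeks after dosing ends (6.4). That is a real cost. Against it, 8 weeks is the only time for which the plan has a reference, and the last time at which recurrence is examined in clinic.

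**Conclusion.** The concern holds in two parts. First, the reference is fixed at 8 weeks, while the primary assessment runs to a self-reported 12-week contact and no section names the one that counts. Following section 2 cumulatively biases the comparison against imiquimod, by 10 percentage points for each late recurrence among ten subjects. Second, the completers-only rule in 7.3 contradicts 4.3, 4.4.1 and section 6 and can discard known outcomes, with an effect in either direction.

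This should be corrected before outcomes are seen, but it does not invalidate the sample-size calculation. The intervals assume the exact method. The counts are illustrative, although 2 or 3 recurrences are about what the planned 25% implies for 8 to 10 subjects (0.25 × 8 = 2; 0.25 × 10 = 2.5). The effects attributed to 7.3 assume that a missed call, or stopping early, makes a subject a non-completer, which 7.3 leaves open.

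**What to change.** **Time point (2, 3.2, 7.2).** Define the primary rate as recurrence at any clinic examination up to 8 weeks after excision (Visit 5), with response meaning no recurrence. The 70% recurrence reference is then 30% response. This matches 7.1, whose calculation of 8 and 10 stays as it is. Report the 12-week phone result as secondary and do not set it against the 8-week 70%.

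**Population (7.3).** Among subjects who had the excision and whose keloid diagnosis was not overturned:

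- (a) a recurrence recorded at or before 8 weeks counts, even without Visit 5;
- (b) a subject examined at Visit 5 is analysed, even if the call is missed;
- (c) a subject with neither is shown under both assumptions. For example, 2/8 observed plus two such subjects runs from 2/10 (2.5–55.6%) to 4/10 (12.2–73.8%).

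Subjects never excised, or found to have another diagnosis, cannot have a keloid recurrence and fall outside these rules. Reconcile 7.3 with 4.3, 4.4.1 and section 6 on the data of withdrawn subjects.

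**Availability.** No change to the 10-week criterion is needed. At most, state that it counts from Visit 1 and so covers Visit 5.

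**Alternative.** If 12 weeks is made primary instead, the sponsor must supply an excision-alone rate for that time and restate 7.1.

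**Cost.** Wording only, with no new visits. The 8-week primary is shorter than every follow-up in Table 1 (12 weeks to 12 months), which the secondary 12-week rate covers in part.
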